4.2 SCIENTIFIC RATIONALE FOR STUDY DESIGN

Control is observation and best medical management for the carotid occlusion which is the standard of care.

4.3 JUSTIFICATION FOR DOSE

Not applicable here.

4.4 END OF STUDY DEFINITION

- 1) Successful completion is 1-year cognitive assessment
- 2) Early termination due to intracranial hemorrhage, stroke, death, seizure or injury to cervical ICA

5 STUDY POPULATION

5.1 INCLUSION CRITERIA

- Age \geq 21
- Complete occlusion of cervical ICA on imaging studies (MRA or CTA) and confirmed with DSA
- History of TIA or stroke
- Increased MTT and/or TTP on CTP as defined as TMax threshold of $> 10\text{cc} > 4$ seconds in the territory of the occluded carotid specifically in the MCA territory when compared to the opposite unaffected hemisphere
- All occlusion is due to atherosclerotic disease
- MoCA < 26 and/or one abnormal test on the rest of the neuropsychological battery administered at screening
- Occlusion is class A or B using COICA classification
- Study team able to gain consent from subject or LAR
- 7. Failed best medical treatment (continued TIA symptoms despite medical management)

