2. TIA: New neurological deficits that resolve within 24 hours of onset and within 120 days prior to enrolment.
3. Abnormal neuropsychological test: any tests included in the screening battery that is scored below 1.5 SDs below the gender, age, and education matched norms.

Procedure:

Procedure will be performed under general anesthesia. Prior to induction of general anesthesia, A-line will be placed to monitor for blood pressure. The mean arterial pressure (MAP) will be maintained above 80mmHG during the procedure till complete revascularization of the occluded cervical ICA. At that time MAP will be lowered to < 80mmHG. The anesthesia team will use their standard of care medications to maintain the pressure as described above.

The groin area will be prepped and draped in the usual sterile fashion. Femoral access will be obtained using 18 gauge needle. Nine French sheet will be placed over the guide wire provided. 5 French Bernstein catheter and 6 French Cook shuttle catheter will be advanced over 0.038 Terumo guide wide to the common carotid artery of the occluded cervical ICA. At the time, the 5 French Bernstein catheter will be withdrawn and contrast will be injected to obtain selective images. After that, attempt to cross the occluded segment will be done, first using SL-10 microcatheter and 0.014 synchro soft microwire, if unsuccessful, then will use the 0.038 exchange Terumo guide wire. If not successful, then will use the stiffer end of the 0.038 exchange Terumo guide wire. If not successful, then abort procedure. If successful, then advance the microwire or the Terumo wire across the occlusion till identifying normal lumen. Following that, angioplasty and stenting using approved angioplasty balloons and carotid stents will be used to recanalize the occluded ICCA. During that time, anesthesia will monitor for bradycardia. If any bradycardia, they treat per standard care and use atropine. Once recanalization is achieved, the MAP will be lowered to < 80mm Hg using standard care medication per anesthesia. IV maintenance dose Tirofiban (0.1 microgram/kg/min) immediately post procedure as a monotherapy for the first 24 hour. Following that the puncture site will be closed using angioseal device. The patient will be extubated and transferred to surgical ICU for BP monitoring. If the subject is doing well, he/she is transferred to the normal floor. Aspirin and plavix will be continued for 12 months.

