We selected a battery of tests that includes a standard screening measure (the MoCA), to facilitate comparisons to other studies that have used this as the primary cognitive outcome measure. The battery includes a number of well-standardized, widely used cognitive tests that measure various aspects of cognitive and behavioral functioning, including intelligence, attention, processing speed, memory, speech and language, visuoconstruction, and executive functioning. We selected a set of tests that can be administered in a one-hour session, and that are highly efficient (providing the highest yield for time required). Also, for all of these tests we have standardized information about the effects of repeat assessment, and/or multiple forms of the tests that allow practice effects to be either obviated or measured and factored into the analyses. A general reference for the neuropsychological assessment battery we are proposing is Lezak, Howieson, Bigler, and [name] (2012)⁵³, the standard textbook on neuropsychological assessment on which one of the current co-investigators ([name]) is a co-author.

The test battery at each time point will include the following measures:

1. Montreal Cognitive Assessment (MoCA): This is a widely used screening instrument designed for the detection of cognitive impairment ⁶². Total points possible on this test range from 0 – 30.
2. Wide Range Achievement Test-5 (WRAT-5)¹⁰⁴, Word Reading subtest: This is a single-word oral reading test, well-validated as an estimate of baseline general intelligence (Wilkinson & Robertson, 2017). The number of correctly read words is converted to an age-adjusted standard score (mean = 100, standard deviation = 15).
3. Wechsler Adult Intelligence Scale – IV (WAIS-IV), Digit Span subtest: This test measures complex attention and working memory. The participant is asked to repeat a series of aurally presented digits of increasing length (a) verbatim, (b) in reverse order, and then (c) sequentially from lowest to highest ¹⁰². The total score is converted to an age-corrected scaled score (mean = 10, standard deviation = 3).
4. WAIS-IV, Coding subtest: This test measures sustained attention and processing speed. Using a key, the participant writes the symbol corresponding to its number as quickly and accurately as possible. The total score is converted to an age-corrected scaled score (mean = 10, standard deviation = 3).

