9.2 SAMPLE SIZE DETERMINATION

To maximize success of the intervention, we will only enroll subjects with classification of A, B, or C. The current success rate for revascularizing types A & B using EVT is 100% and type C using the Hybrid technique is 80% making the success rate for the whole sub-cohort is 93%. Based on our preliminary data and others, the mean difference in the pre- and post-procedure MoCA score was between 5-8 points. Using two comparisons: A) comparison between intervention vs. best medical management and B) pre- and post-intervention for successful vs unsuccessful intervention. We pooled the data for these studies, and then used the lower and upper ends of the confidence interval calculated between the suggested groups for the trial (best medical management vs. intervention). Doing so, we will assume the difference between pre- and post-procedure MoCA score to be 2 points and standard deviation to be 2 points. Assuming $\alpha=0.05$; $\beta=0.8$; and power of 80%, then our total sample size needed is 34 (Table 2). Based on our previous clinical trial experiences, we anticipate maximum of 10% drop out. Given that, then total sample size needed is 38 subjects with 19 subjects in each group.

Sample size estimates: Total N						
MoCA Score	Difference in total points between pre and post procedure	1		2		3
		1	2	1	2	1
	Standard Deviation difference between pre & post procedure	1	2	1	2	1
	Power :					
0.8		34	128	5	34	6
0.85		38	146	12	38	8
0.9		46	172	14	46	8
0.95		54	210	16	54	8
						26

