9.4.2 ANALYSIS OF THE PRIMARY EFFICACY ENDPOINT(S)

Primary Endpoint: Montreal Cognitive Assessment (MoCA) and cognitive battery of tests. They will be administered by a neuropsychologist masked to treatment at the pre-treatment, at 3 month and 12 month assessments. The battery is designed to assess left hemisphere function, right hemisphere function, and global function. All tests had published age-adjusted norms

10,12,38,59,60,76,80,95,101,108. All subjects will undergo all 14 cognitive tests. The order of test administration will remain constant, accommodating the delays required for recall intervals and minimizing stimulus interference in memory tasks. The raw score for each test for each subject will be converted into test-specific z score for each test in the battery. Then a composite z score based on average z score for the tests for each subject (sum of the z scores divided by the number of tests included) will be calculated. A two-sided type I error rate of 0.05 will be used.

A linear mixed effect model (PROC MIXED in SAS, Version 9.4) will be used to compare the two groups (medical management vs. surgical intervention) with the change in MoCA as the dependent variable across the repeated measures of 6 months and 12 months. The main independent variable is the intervention. The multivariable model will be adjusted for the following covariates: age, gender, education level (\leq 8th grade, 9th–12th grade [high school], or \geq 13 years [some college]), ICA side, and pre-treatment depression (as measured by the Center for Epidemiologic Studies–Depression scale). The correlation coefficient between MoCA change and the composite cognitive score will be calculated. A second comparative model of the interventions will be performed to support the primary analysis. It will use the change in composite cognitive z score as the dependent variable. Similar analysis using mixed linear models and covariates will be done.

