10.3 PROTOCOL AMENDMENT HISTORY

The table below is intended to capture changes of IRB-approved versions of the protocol, including a description of the change and rationale. A Summary of Changes table for the current amendment is located in the Protocol Title Page.

Version	Date	Description of Change	Brief Rationale
V3.0	8/13/20	Revision to study design to reflect I/E adjustment	Including changes to make study endpoints consistent with I/E criteria
V3.0	8/13/20	Change 3 month visit to 6 month follow up	Makes study protocol more consistent with surgical/ clinical procedures
V3.0	8/13/20	Inclusion/ exclusion criteria adjusted	Includes more subjects and reflects issues we have faced so far with recruitment
V3.0	8/13/20	Added blood draw, if subject is randomized to intervention	
V4.0	1/25/21	Updated study to include study arm 3	Allows study to follow subjects who are relevant to study aims but not eligible for treatment
V4.0	1/25/21	Inclusion/ exclusion criteria adjusted	Includes subject who are impaired but do not show impairment on MoCA
V4.0	1/25/21	Updated MRI protocol	Allows study team to measure white matter integrity.
V4.0	2/4/2021	Added 6 month MRI	Allows the study team to compare 6 months post op
V5.0	5/15/2021	Inclusion of DSA to confirm COICA classification	Definitive COICA classification
V5.0	5/15/2021	Inclusion/ exclusion criteria adjusted	Based on DSMB recommendations
V5.0	5/15/21	Further definition of 3 rd non-randomized arm	Necessitated by adjustments to I/E criteria
V.50	5/15/2021	Inclusion of adjudicators to confirm eligibility of surgical arm	Included to minimize surgical risk
V5.0	6/21/21	Adjusted stopping rules	Protocol adherence with DSMB ruling
V6.0	9/3/21	Added Co-PI [name] study requirements
V6.0	9/3/21	Inclusion criteria adjustment	Provided specifications on MTT/TTP measurements
V6.0	9/3/21	Removed inaccurate wording of primary objective	Clerical mistake corrected
V6.0	9/3/21	Clarified AE reporting workflow	Included for more thorough team roles
V6.1	10/12/21	Wording changes for medical management	Promoting clarity and consistency
V6.1	10/12/2021	Defined Visit windows	Promoting clarity and consistency

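### Patients with a normal MoCA (26-30) can be randomised, yet the first efficacy model and the sample size use MoCA change with no ceiling allowance and no baseline-MoCA covariate

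*Combined protocol and SAP*

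**What the plan says.** **Entry.** Section 5.1 requires "MoCA < 26 and/or one abnormal test on the rest of the neuropsychological battery administered at screening". The table in 5.5 excludes a MoCA of 26 or more only when the screening battery is also normal. Section 4.1 defines the qualifying abnormal result as "any tests included in the screening battery that is scored below 1.5 SDs below the gender, age, and education matched norms". Section 10.3 shows that this was intended; the rationale recorded for a V4.0 change is "Includes subject who are impaired but do not show impairment on MoCA".

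**Outcome.** Section 4.1 gives the MoCA a range of 0 to 30. In 9.4.2 the first mixed model takes change in MoCA at 6 and 12 months as the dependent variable. A second model, on change in the composite z score, supports it.

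**Covariates.** Section 9.4.2 states: "The multivariable model will be adjusted for the following covariates: age, gender, education level". The list goes on to ICA side and pre-treatment depression and ends there. The composite model uses similar covariates. Neither baseline MoCA nor baseline composite z is named.

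**Sample size.** Section 9.2 rests on the MoCA alone: "we will assume the difference between pre- and post-procedure MoCA score to be 2 points and standard deviation to be 2 points". With alpha 0.05 "and power of 80%, then our total sample size needed is 34", raised to 38 for 10% drop-out.

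**The concern.** The plan admits some patients because the MoCA does not show their impairment, and then measures benefit first on the MoCA. A patient entering at 30 cannot gain, one at 29 can gain 1 point, and one at 28 has exactly the planned 2 points. At 26 or 27 there are 4 or 3 points of room, but the cap still clips the upper part of the distribution of change, more so in the arm that improves more.

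The controlled study in Table 1 (section 2.2), cited for the MoCA effect, had mean baselines of 14.67 and 14.91, about 15 points below the ceiling. Section 9.2 does not adapt its 2-point assumption to patients entering at 26-30.

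At stake are two things: power that is lower than stated by an amount the plan does not acknowledge, and precision given up in a trial of 38 by leaving out a baseline value that is collected anyway.

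**Working it through.** **Inputs.** From 9.2: difference 2, SD 2, 34 evaluable, 10% drop-out. From 9.4.2: "A two-sided type I error rate of 0.05 will be used". From 4.1: maximum score 30. From Table 1: baseline SDs 3.56 and 3.39, 6-month SDs 2.85 and 2.97, rounded here to 3.5 and 2.9. Assumed, because the documents do not say: the share entering with MoCA 26-30 (10, 30, 50%), their entry scores (uniform on 26-30), the other entry scores (uniform on 18-25) and the control-arm change (0 or 2 points).

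**1. The plan's own figure.** Normal approximation: 2 × (1.96 + 0.84)² × 2²/2² = 15.7, so 16 per arm. The two-sample t-test needs 17 per arm, total 34, power 80.7%. Then 34/0.9 = 37.8, so 38. Section 9.2 is reproduced.

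**2. Effect of the cap by entry score.** Let latent change be normal with mean m and SD 2, and let r = 30 − entry score. With a = (r − m)/2, the mean observed change is mΦ(a) − 2φ(a) + r[1 − Φ(a)]. The observable effect is this value at m = c + 2 minus its value at m = c, where c is the control change.

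Example, entry 28 and c = 0. Intervention: 2(0.5) − 2(0.399) + 2(0.5) = 1.20. Control: 0 − 2(0.242) + 2(0.159) = −0.17. Difference: 1.37.

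| Entry MoCA | Room | Effect, c = 0 | Effect, c = 2 |
|---|---|---|---|
| 26 | 4 | 1.85 | 1.37 |
| 27 | 3 | 1.66 | 1.00 |
| 28 | 2 | 1.37 | 0.63 |
| 29 | 1 | 1.00 | 0.34 |
| 30 | 0 | 0.63 | 0.15 |
| Mean, 26-30 | | 1.30 | 0.70 |

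At 23 or below the loss is at most about 0.05. The effect at 30 is not zero because the model lets scores fall and a benefit can prevent a fall.

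**3. Power at 17 per arm.** Simulated follow-up scores capped at 30, with a t-test on change. The cap is allowed to alter the SD as well as the mean.

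| Share with MoCA 26-30 | c = 0 | c = 2 |
|---|---|---|
| 10% | about 79% | about 73% |
| 30% | about 75% | about 61% |
| 50% | about 72% | about 49% |

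Rounding the simulated scores to whole points or leaving them continuous moves these by about 1 percentage point.

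**4. What a baseline covariate would do.** The variance of change is 3.5² + 2.9² − 2r(3.5)(2.9) = 20.66 − 20.3r, where r is now the correlation of baseline with follow-up. A change SD of 2 requires r = (20.66 − 4)/20.3 = 0.82. At r = 0.82:
- variance of change: 20.66 − 16.65 = 4.01;
- residual variance after adjustment: 2.9² × (1 − 0.82²) = 8.41 × 0.3276 = 2.76;
- reduction: 1 − 2.76/4.01 = 31%;
- slope of follow-up on baseline: 0.82 × 2.9/3.5 = 0.68, so a 1-point chance imbalance shifts the change contrast by 1 − 0.68 = 0.32 points, against the arm with the higher baseline.

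A correlation of 0.5 would give a 40% reduction, but it implies a change SD of √10.51 = 3.2, which conflicts with the plan's 2.

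**5. A MoCA <26 analysis.** At a 30% share, 0.7 × 17 = 11.9, about 12 per arm. For a 2-point difference and SD 2, power is about 65%.

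**The case against.** **The battery is also primary.** Sections 1.1, 3, 4.1 and 9.1 name the 14-test battery including the MoCA, and 9.4.1 lists a battery summary score beside MoCA change. A reader might infer that MoCA change is the only primary measure; the documents do not support that. The composite may capture impairment that the MoCA misses. What stands is that 9.2 powers only the MoCA and 9.4.2 gives the composite a supporting role.

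**Randomisation protects the comparison.** This is correct. A reader might infer that omitting baseline MoCA biases the estimate, or that a chance imbalance passes through in full. Neither follows: the change score already subtracts baseline, and about a third of an imbalance remains. The omission is a loss of precision.

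**A null result would still be readable.** Section 9.4.8 tabulates individual cognitive measures at baseline, 6 and 12 months, so headroom would be visible. It would be too strong to say that a null could not be told apart from lack of room.

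**The entry route may look looser than it is.** One might infer that a patient could qualify on mood alone through the BDI-FS. The abnormality rule needs a score below matched norms, whereas the BDI-FS is reported in severity bands, lies outside tests 2-12 that are converted to z scores, and is used as a covariate. WRAT-5 Word Reading is different. Section 4.1 says of it: "This is a single-word oral reading test, well-validated as an estimate of baseline general intelligence". The literal definition could admit a patient on it, but the contents of the screening battery are not listed, so this is not established and the point does not rest on it.

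**Conclusion.** The concern holds in a bounded form. Patients with MoCA 26-30 can be randomised, the first model and the sample size use a score capped at 30, and neither model adjusts for its own baseline.

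The strict lack of room applies only to entry at 29 or 30. The loss of power is modest if controls do not change and substantial only if many patients enter this way and controls also improve. Its true size cannot be fixed from the documents, because they give neither the share nor the expected control change. The figures also treat the entry score as error-free and assume the same latent 2-point benefit at every entry score.

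The 31% gain from adjustment rests on SDs like those in Table 1 and on the correlation implied by the planned change SD. It is separate from the ceiling: a covariate sharpens the estimate and removes the effect of chance imbalance, but restores no headroom.

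**What to change.** 1. **Section 9.4.2.** Add continuous baseline MoCA as a covariate in the MoCA model and baseline composite z in the composite model. Cost: one degree of freedom in each model and no new data.
2. **Section 9.4.2.** Prespecify the 12-month MoCA effect in randomised patients with baseline MoCA below 26 as a supportive analysis, noting its limited power (about 65% with 12 per arm), so that a null there is not over-read. Cost: SAP wording.
3. **Section 9.2.** State that the 80% power assumes no ceiling loss, and show the range for plausible shares with MoCA 26-30. Cost: a short paragraph.

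Optional: list the screening battery in 4.1, 5.1 and 5.5 and say which tests can qualify a patient, including whether WRAT-5 counts. This is a clarification and does not cure the ceiling, since a patient at 30 could still enter on another test.

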5.2 EXCLUSION CRITERIA

- History of Moyamoya or Moyamoya like disease
- Tandem occlusion
- No evidence of increased MTT or TTP on CT perfusion \diamond

- Severe co-morbid diseases: renal insufficiency, end-stage renal disease, liver cirrhosis, COPD requiring home oxygen, terminal illness such as cancer, Parkinson disease or other neurodegenerative diseases, severe cognitive heart failure, seizures, debilitating stroke, mRS ≥ 3 .
- Short life expectancy due to cancer or other co-morbid diseases
- Class C or D on COICA classification [◊]
- Occlusion of the Common Carotid Artery
- Normal neuropsychological battery results [◊]
- Subject unwilling to participate in follow up and/ or unwilling to be randomized to surgery [◊]

◊ If subject meets any combination of these exclusion criteria, they may be applicable for the non-randomized third arm.

If a subject meets all criteria and is randomized to surgery their eligibility will be confirmed by 1 outside adjudicator. If this decision is not in agreement with the PI then a second adjudicator will review. Despite ruling, inclusion will be confirmed by two clinicians (PI and adjudicator or both adjudicators).

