1.2 SCHEMA

1.3 SCHEDULE OF ACTIVITIES (SOA)

The schedule below is provided as an example and should be modified as appropriate.

Procedures	Screening Day -30 to -1	Enrollment/Baselining Visit 1, Day 0 ^f	Study Visit 4 6 Months +/- 6 weeks	Final Study Visit 12 months +/- 6 weeks
Informed consent	X			
Demographics	X			
Medical history	X			
Randomization ^a	X			
Administer study intervention		X ^e		
Concomitant medication review	X		X	
Physical exam (including height and weight)	X	X	X	X
Vital signs	X	X	X	X
Height	X			
Weight	X			
Performance status	X			
Hematology	X			
Serum chemistry ^a	X			
Pregnancy test ^b	X			
Blood Test ^c		X		
EKG (as indicated)	X			
Adverse event review and evaluation	X		X	
CTP	X	X		
MRA or CTA	X			
Radiologic/Imaging assessment (MRI of the brain)	X		X	X
Cognitive testing	X		X	X
Complete Case Report Forms (CRFs)	X	X	X	X
Diagnostic angiogram	X ^d			X ^c
Medication check			X	X

a- Not applicable to 3rd study arm

b- Only if necessary, to confirm surgery eligibility

c- Surgical arm only

d- Only applicable if the subject has not had one in the past 6 months

e- Prior to surgical intervention eligibility will be confirmed by adjudicator(s)

f- Enrollment for surgical arm may be delayed due to OR schedule

- g- 6-month follow up visit timeframe is based on the date of randomization for non-surgical date of surgery for surgical arm
- h- 12-month follow up visit timeframe is based on same dates as 6-month visit

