2 INTRODUCTION

2.1 STUDY RATIONALE

Complete occlusion of the Internal carotid artery (ICA) by atherosclerotic disease (COICA) causes approximately 15%–25% of ischemic strokes in the carotid artery distribution. (11,17,48,54,57,70,71,84,92,98) Patients treated with medical therapy have a 7%–10% risk of recurrent stroke per year for any stroke and a 5%–8% risk per year for ipsilateral ischemic stroke during the first 2 years after ICA occlusion. (41,42,46,49,50,68,69) Internal carotid artery occlusion causes an estimated 61,000 first-ever strokes per year in the US (1,15,34,57,70,92,105) an incidence more than twice the annual occurrence of ruptured intracranial aneurysms (14) Additionally, 40% of subjects with COICA who present with TIA and 70% of COICA who present with stroke have cognitive decline with increased risk of vascular dementia and Alzheimer's disease (AD) with time (2,3).

Symptomatic COICA subjects are at increased risk of developing cognitive impairment and progressive development of vascular dementia and AD with time. Our proposal leverages several compelling retrospective and prospective preliminary data from human to perform this exploratory trial with go/no-go criteria to proceed to a phase 3 based on the data generated

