4 STUDY DESIGN

4.1 OVERALL DESIGN

Primary Hypothesis:

Revascularizing symptomatic chronically occluded cervical ICA (COICA) using endovascular techniques will significantly improve cognitive outcome.

Primary Objective:

To test the hypothesis that endovascular revascularization of COICA (via endovascular techniques) improves significantly cognitive function assessed by a specifically designed battery of 14 cognitive tests including the MoCA.

Secondary Objectivs:

To test the safety of endovascular revascularization of chronically occluded ICA.

Tertiary/Exploratory Objectives:

To test the hypothesis that subjects with symptomatic COICAs and mild/moderate cognitive dysfunction have the following biomarkers:

- A) increased MTT or TTP on CTP in the ipsilateral side of the occluded ICA specifically in the MCA territory when compared to the opposite unaffected hemisphere
- B) Presence of lactate and decreased Naa/Cr in the watershed area (specifically centrum semiovale) on 1H-MRI-spectroscopy, and
- C) Decreased size of the hippocampus and amygdala on MRI.

Primary endpoints:

Cognitive outcome at 12-month follow-up assessed mainly by a specifically designed battery of 14 cognitive tests including MoCA.

Secondary endpoints:

1. Safety: Occurrence of Stroke, Cerebral Hemorrhage, or Death

Exploratory endpoints:

Biomarkers:

- A) The presence/absence of lactate on 1H-MRI spectroscopy in centrum semiovale in the ipsilateral side of COICA;
- B) The change in size of amygdala and hippocampus in the ipsilateral side of COICA.
- C) Improvement/ normalization of MTT and/or PTT on CTP specifically in the ipsilateral MCA territory.
- D) subgroup difference (Gender)

Study Design:

This is a phase 2 randomized single-center open label clinical trial with randomization of 1:1 to either best medical management vs. best medical management and endovascular revascularization of COICA. Subjects who meet all inclusion criteria but have a normal CTP may be included in the unrandomized prospective observational 3rd arm.

Intervention: Surgical intervention - endovascular balloon angioplasty and stenting

Protocol:**Screening, Enrolling, & Randomization:**

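### Outside eligibility review comes after open-label randomisation and in the surgical arm only, and the plan does not secure follow-up of the patients it rejects

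*Combined protocol and SAP*

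**What the plan says.** - **Design (4.1):** "This is a phase 2 randomized single-center open label clinical trial with randomization of 1:1". Section 6.2 blinds the assessment of cognition, MRI and exploratory endpoints. It does not mention eligibility decisions.
- **Adjudication (5.2):** "If a subject meets all criteria and is randomized to surgery their eligibility will be confirmed by 1 outside adjudicator". If that adjudicator disagrees with the PI, a second one reviews. Whatever the ruling, "inclusion will be confirmed by two clinicians (PI and adjudicator or both adjudicators". What follows a ruling of ineligible is not stated.
- **Timing (1.3):** randomisation is listed at screening, and footnote e reads "Prior to surgical intervention eligibility will be confirmed by adjudicator(s". The amendment history (10.3, V5.0, May 2021) ties adjudication to the surgical arm and gives its purpose as minimising surgical risk.
- **Withdrawal and replacement (7.2):** the investigator may withdraw a participant who meets an exclusion criterion, including one that was missed earlier. Subjects who are randomised but do not receive the study intervention may be replaced. Neither rule names an arm, and 6.1.1 lists medical management as well as stenting.
- **Visit clock (1.3, footnotes f to h):** "Enrollment for surgical arm may be delayed due to OR schedule"; "6-month follow up visit timeframe is based on the date of randomization for non-surgical date of surgery for surgical arm"; "12-month follow up visit timeframe is based on same dates as 6-month visit". Cognitive Testing in 4.1 and 8.1 counts from hospital discharge instead, and 7.3 counts from the intervention.
- **Analysis (9.3, 9.4.1):** ITT is stated twice and not defined.

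**The concern.** Randomisation makes the arms comparable only if whatever happens afterwards to decide who is followed and analysed applies equally to both. Here one arm gets a second eligibility judgement, made by people who know the allocation because they are consulted only for patients allocated to surgery. A patient with the same features allocated to medical management is never re-examined. A negative ruling yields just the kind of late-recognised exclusion that 7.2 accepts as a reason for withdrawal. A patient who is not operated on may also be replaced.

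On paper 7.2 covers both arms. In practice it falls mainly on the surgical arm, which alone faces adjudication and a wait for theatre. If such patients drop out of the 12-month assessment, the surgical mean rests on a filtered group and the medical mean on an unfiltered one. The trial describes itself as an "exploratory trial with go/no-go criteria to proceed to a phase 3", so a distorted estimate would feed that decision.

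**Working it through.** **Inputs from the plan (9.2, 9.4.2).** Difference 2 MoCA points, SD 2, two-sided alpha 0.05, power 80%, N = 34 before and 38 after 10% drop-out, 19 per arm.

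**Plan's own figure.** With 17 per arm, SE = 2 × √(2/17) = 0.686. The noncentral t (32 df) gives power 80.7%, so total N = 34 reproduces. 34 / 0.9 = 37.8, giving 38.

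**Assumed, because the documents give neither.** The number of the 19 surgical patients lost, k, and how far their 12-month MoCA change differs from the rest, d. Three pairs (k, d) are shown: (1, 2), (2, 3) and (4, 4).

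**Bias = (k/19) × d, in either direction**
- 1/19 × 2 = 0.11 points
- 2/19 × 3 = 0.32 points
- 4/19 × 4 = 0.84 points

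**Type I error if the lost patients would have done worse.** Simulation of 200,000 trials, t-test, 17 per arm, within-class SD 2. The medical arm keeps the affected share k/19 and the surgical arm loses it.

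| k, d | lost and replaced | lost, not replaced | all kept |
|---|---|---|---|
| 1, 2 | 5% | 5% | 5% |
| 2, 3 | 7% | 7% | 5% |
| 4, 4 | 17% | 14% | 5% |

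**Power at a true 2-point effect if the lost patients would have done better.** Same model. The effect is held at 2 points in everyone analysed, to separate selection from dilution. The comparator must be the same mixed population with everyone retained, because the subgroup gap itself adds variance.

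| k, d | all kept | lost and replaced |
|---|---|---|
| 1, 2 | 79% | 75% |
| 2, 3 | 73% | 62% |
| 4, 4 | 59% | about 30% |

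**Cost of keeping adjudication late but analysing everyone as randomised.** If unoperated patients gain nothing over medical management, 10% or 20% untreated reduces the expected effect to 1.8 or 1.6 points. Power at 17 per arm falls from 80.7% to 72.1% or 61.9%.

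**The case against.** The strongest reply is that loss is inferred, not planned. ITT conventionally means all randomised patients as allocated, replacing a subject does not by itself delete that subject's data, and 4.1 arranges 6- and 12-month visits for those randomised. This stands in part. A reader might infer that the plan removes rejected patients from the analysis; no passage says so. But ITT cannot supply scores that were never collected, and nothing obliges the site to collect them.

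The 5.2 procedure also limits rejections. It appears that a patient the PI considers eligible is rejected only if both outside adjudicators disagree with the PI. Adjudication entered at V5.0, and 2.3.3 refers to complication rates in the trial to June 2021, so some surgical patients may never have faced it. Both points stand. They make 1 or 2 losses more plausible than 4.

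On the clock, non-surgical in footnote g could be read to cover a surgical-arm patient who was not operated on, and an aborted procedure still has a date. The gap therefore concerns only patients never taken to the procedure. Choosing randomisation over surgery as the start for everyone is partly a preference.

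A reader might also infer that the bias favours surgery, since adjudication was introduced to reduce surgical risk. No passage links surgical risk to 12-month MoCA change, so the sign cannot be settled. Nor should power in the extreme case be set against the planned 80.7%: much of that fall comes from the assumed subgroup gap, not from losing patients.

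**Conclusion.** The point holds as a fault in design and wording that is worth fixing. Eligibility is re-judged after allocation is known, in one arm only. The withdrawal and replacement rules give rejected patients a way out, and no provision secures their 12-month data. One-sided loss is permitted, not prescribed, and its direction is unknown.

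The size is illustrative and rests on the assumed k and d. For 1 or 2 losses the bias is about 0.1 to 0.3 MoCA points, with type I error of 5% to 7% or, in the other direction, a power loss of roughly 4 to 11 percentage points. At the low end this is negligible. The 17% type I error needs 21% of the surgical arm rejected and a gap of two SDs, which the 5.2 procedure makes unlikely.

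**What to change.** 1. **5.2 and 1.3:** have the existing adjudicators confirm trial eligibility for every candidate before allocation is revealed. Any later pre-surgery safety check can stay, but it should not end follow-up or remove a patient from the analysis.
2. **7.2 and 9.3:** delete replacement of randomised subjects, or state that replaced subjects are still followed and analysed. State that an exclusion criterion recognised after randomisation does not end the cognitive visits. Define ITT as all randomised patients in their assigned arm.
3. **1.3, 4.1, 7.3 and 8.1:** give surgical-arm patients who are never operated on a visit date counted from randomisation, preferably by timing both arms from randomisation, and reconcile the four sections.

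**Cost.** No sample-size input changes, so N stays at 38. Reviews rise from 19/(1 − r) to 38/(1 − r), where r is the share rejected. That is 19 more with no rejections, 20 at r = 1/19 and 24 at r = 4/19, by the existing adjudicators. A few more candidates may have to be screened. The added time cannot be fixed, because 7.2 does not say how replacements are allocated. If they go straight into surgical places, the present plan needs 19 + 19/(1 − r) = 39.1 or 43.1 candidates, against 40.1 or 48.1 under the proposal. If they are randomised 1:1, both need 40.1 or 48.1 and the difference vanishes. Where surgery is delayed, a randomisation clock shortens post-surgical follow-up; the six-week visit window absorbs short delays.

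If adjudication must stay after randomisation, items 2 and 3 still close the loss route. The plan should then state the lower power, about 72% or 62% with 10% or 20% of the surgical arm untreated.
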